### **9.6.2 Statistical Methods for Safety Analyses**

The proportion of participants with AEs resulting in discontinuation from study and any SAEs will be reported and summarized descriptively. The point estimates and the 95% CIs will be calculated using the Clopper Pearson method [Collett, D. 1999].

## **9.7 Interim Analyses**

No interim analyses are planned for this study.

## **9.8 Multiplicity**

No statistical hypothesis testing will be performed for immunogenicity analyses in this study. Therefore, no multiplicity adjustment is required in this study.

## 9.9 Sample Size and Power Calculations

### 9.9.1 Sample Size and Power for Immunogenicity Analyses

Since this is an estimation study, no formal power calculation for immunogenicity was performed. This study will enroll approximately 200 participants and will allow estimation of the primary immunogenicity endpoint with a 95% CI with a half-width of 4.0 percentage points. This is based on the following assumptions: 1) approximately 200 participants enrolled, 2) an underlying response rate of 95%. The calculation is based on the exact binomial method proposed by Clopper and Pearson [Collett, D. 1999]. In order to evaluate the potential impact of limited enrollment and attenuated response rate, the half-width of the 95% CI is evaluated under different sample size and response rate assumptions. [Table 3](#) summarizes estimates of the half-width of the CI under various sample size and response rate.

Table 3 Estimates of the Half-width of the 95% Confidence Interval Under Different Assumptions

Evaluable Sample Size	Assumed Response Rate		
	85%	90%	95%
125	7.5%	6.6%	5.4%
150	6.7%	6.0%	4.7%
175	6.1%	5.4%	4.4%
200	5.7%	5.0%	4.0%
225	5.4%	4.7%	3.7%

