### **9.6.1 Statistical Methods for Immunogenicity Analyses**

This section describes the statistical methods that address the immunogenicity objectives. No statistical hypothesis testing will be performed for immunogenicity analyses in this study. Point estimates and 95% CIs will be provided for both the primary and secondary immunogenicity objectives.

The point estimate for the primary immunogenicity objective will be calculated as the proportion of participants with a protective anti-HBs level of  $\geq 10$  mIU/mL at 30 days post-challenge with HBVAXPRO™. The CIs will be calculated based on the exact method proposed by Clopper and Pearson [Collett, D. 1999].

The point estimates for the secondary immunogenicity objective will be calculated by exponentiating the estimates of the mean of the natural log values. The 95% CIs will be derived by exponentiating the bounds of the CIs of the mean of the natural log values based on the t-distribution.

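### The 4.0-point half-width in Section 9.9.1 and all 15 cells of Table 3 are distances to the lower confidence limit; the half-width at n=200 and 95% is 3.3 points

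*Combined protocol and SAP*

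**What the plan says.** Section 9.9.1 makes no power claim, because this is an estimation study. It justifies the size of the study by precision: the trial "will allow estimation of the primary immunogenicity endpoint with a 95% CI with a half-width of 4.0 percentage points". The stated assumptions are "approximately 200 participants enrolled" and a true response rate of 95%. On method it says: "The calculation is based on the exact binomial method proposed by Clopper and Pearson".

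Table 3 extends this to evaluable sample sizes of 125 to 225 and response rates of 85%, 90% and 95%. Its title is "Estimates of the Half-width of the 95% Confidence Interval Under Different Assumptions", repeated in the List of Tables, and the lead-in sentence says that it "summarizes estimates of the half-width of the CI under various sample size and response rate". The cell for n=200 and 95% is 4.0%, as in the text.

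Section 9.6.1 plans the same interval for the primary analysis: "The CIs will be calculated based on the exact method proposed by Clopper and Pearson". No section defines half-width as anything other than half the length of the interval.

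**The concern.** A Clopper-Pearson interval for a proportion near 95% is not symmetric: its lower arm is clearly longer than its upper arm. A half-width is half the distance between the two limits, so it must lie between the two arm lengths. The printed 4.0 looked too large to be that.

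One cell shows the problem without software. At n=125 and 95%, Table 3 gives 5.4. Read as a half-width around 95%, it puts the upper limit at 95 + 5.4 = 100.4%, which no proportion can reach.

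Section 9.9.1 holds the only numerical precision statement for the primary endpoint; the summary in Section 9.1 says only that a 95% CI can be estimated. Anyone who recomputes the figure by the named method gets a different answer, and anyone who applies it as plus or minus 4.0 gets the wrong upper limit.

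**Working it through.** **Inputs**
- Confidence level: 95% (Sections 9.6.1 and 9.9.1), taken as two-sided with 0.025 in each tail.
- Method: Clopper-Pearson (Sections 9.6.1 and 9.9.1).
- Sample sizes n and rates p: the grid of Table 3.
- Responder count x: n × p rounded to the nearest integer, halves up. The plan gives no rounding rule; this is the one under which its numbers reproduce.

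**Formulas**
- Lower limit L = 0.025 quantile of Beta(x, n − x + 1).
- Upper limit U = 0.975 quantile of Beta(x + 1, n − x).
- Lower arm = x/n − L; upper arm = U − x/n; half-width = (U − L)/2.

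**Headline case, n=200 and 95%**
- x = 200 × 0.95 = 190.
- L = 91.00%, U = 97.58%.
- Lower arm = 95.00 − 91.00 = 4.00, which is the plan's 4.0.
- Upper arm = 97.58 − 95.00 = 2.58.
- Half-width = (97.58 − 91.00)/2 = 3.29, or 3.3.

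**All cells of Table 3** (percentage points)

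| n | p | x | Printed | Lower arm | Half-width |
|---|---|---|---|---|---|
| 125 | 85% | 106 | 7.5 | 7.515 | 6.654 |
| 125 | 90% | 113 | 6.6 | 6.569 | 5.555 |
| 125 | 95% | 119 | 5.4 | 5.355 | 4.187 |
| 150 | 85% | 128 | 6.7 | 6.693 | 5.967 |
| 150 | 90% | 135 | 6.0 | 5.957 | 5.126 |
| 150 | 95% | 143 | 4.7 | 4.712 | 3.741 |
| 175 | 85% | 149 | 6.1 | 6.149 | 5.533 |
| 175 | 90% | 158 | 5.4 | 5.383 | 4.668 |
| 175 | 95% | 166 | 4.4 | 4.395 | 3.580 |
| 200 | 85% | 170 | 5.7 | 5.716 | 5.180 |
| 200 | 90% | 180 | 5.0 | 5.021 | 4.403 |
| 200 | 95% | 190 | 4.0 | 4.003 | 3.290 |
| 225 | 85% | 191 | 5.4 | 5.360 | 4.887 |
| 225 | 90% | 203 | 4.7 | 4.651 | 4.100 |
| 225 | 95% | 214 | 3.7 | 3.690 | 3.057 |

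To one decimal, the lower arm agrees with the printed value in 15 of 15 cells and the half-width in 0 of 15.

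**Size of the gap**
- Smallest absolute gap: 5.4 − 4.887 = 0.51 (n=225, 85%).
- Largest absolute gap: 5.4 − 4.187 = 1.21 (n=125, 95%).
- Smallest relative gap: 5.7/5.180 = 1.10, or 10% (n=200, 85%).
- Largest relative gap: 5.4/4.187 = 1.29, or 29% (n=125, 95%).
- Headline cell: 4.0 − 3.29 = 0.71 points; 4.0/3.29 = 1.22, or 22%.

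**Other readings tried**
- Clopper-Pearson half-width with x rounded down, with fractional x, or averaged over the binomial distribution: 0 of 15 each. The averaged value at n=200 and 95% is 3.25.
- Normal approximation without and with continuity correction, and Wilson: 0 of 15 each. At n=200 and 95% they give 3.02, 3.27 and 3.11.
- Clopper-Pearson half-width at 97.5% or 99% confidence: 3 and 1 of 15.

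**The case against.** The strongest reply accepts the arithmetic and disputes its weight. No hypothesis, success criterion or precision target depends on the label. The analysis will report the actual exact interval. The true half-width is smaller than stated, so nothing suggests that 200 participants are too few. In a durability study with a high expected response, the lower limit is the natural planning quantity, and the printed 4.0 gives it correctly as 91.0%. Only the upper limit would be misread, and nothing in the plan uses it. The 29% figure comes from a fallback row; at the planned size the gap is 0.7 points. Finally, the lower arm is the longer arm in every cell, so the authors may have used the longer arm as a deliberately cautious margin.

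Most of this stands and sets the severity: the numbers do come from Clopper-Pearson, and the quantity has the wrong name. It does not remove the error. The plan never says that half-width means the longer arm, and a cautious margin still needs its right name.

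A further objection improves the fix. The table headers show nominal rates, but the printed distances run from x/n. At n=125 and 90%, x/n is 113/125 = 90.4% and the exact lower limit is 83.8%; subtracting 6.6 from the 90% header gives 83.4%. Measured from the nominal rate, only 4 of 15 cells match. Rounding counts down gives 8 of 15, and rounding halves to even gives 13 of 15. A relabelled table therefore needs the rounding rule stated beside it.

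**Conclusion.** The concern holds. The half-width in Section 9.9.1 and every cell of Table 3 are Clopper-Pearson lower-arm distances under the wrong label. At n=200 and 95% the half-width is 3.3 points, not 4.0; across the table the overstatement is 0.5 to 1.2 points. A reader who takes 95% plus or minus 4.0 gets 91.0% to 99.0%, where the stated method gives 91.0% to 97.6%.

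The consequence is small. The error is conservative in every cell, and the number of participants, the conduct of the study and the analysis in Section 9.6.1 are unaffected. It should still be corrected, because it is the plan's only numerical statement of precision for the primary endpoint.

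The conclusion assumes a two-sided 95% interval and the usual meaning of half-width. The identification of the printed values also assumes counts rounded halves up, but under no rounding tried does a 95% Clopper-Pearson half-width match any cell.

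**What to change.** **Preferred.** Keep the numbers and change the label. In the precision sentence and the Table 3 lead-in of Section 9.9.1, in the title of Table 3 and in the List of Tables, replace half-width with the distance from the point estimate to the lower 95% confidence limit. Give the expected interval at 190/200, 91.0% to 97.6%. Add a footnote to Table 3 that responder counts are rounded to the nearest integer, halves up, and that distances are measured from the resulting observed proportion.

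**Alternative.** Keep the term half-width, restate the headline as 3.3 points, and replace Table 3 with these values, with a footnote giving the same rounding rule:

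| Evaluable n | 85% | 90% | 95% |
|---|---|---|---|
| 125 | 6.7 | 5.6 | 4.2 |
| 150 | 6.0 | 5.1 | 3.7 |
| 175 | 5.5 | 4.7 | 3.6 |
| 200 | 5.2 | 4.4 | 3.3 |
| 225 | 4.9 | 4.1 | 3.1 |

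**Optional.** Tie the headline figure to 200 evaluable (per-protocol) participants, as in the Table 3 row header, rather than to 200 enrolled.

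The cost is a text and table correction only, with no change to the sample size, conduct or analysis.

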### 9.9.2 Sample Size and Power for Safety Analyses

The probability of observing at least 1 SAE in this study depends on the number of participants vaccinated and the underlying percentage of participants with an SAE in the study population. If the underlying incidence of an SAE is 0.80% (1 of every 124 participants receiving the vaccine), there is an 80% chance of observing at least 1 SAE among 200 participants. If the underlying incidence of an SAE is 0.35% (1 of every 289 participants receiving the vaccine), there is an 50% chance of observing at least 1 SAE among 200 participants. If no SAEs are observed among the 200 participants, this study will provide 95% confidence that the underlying percentage of participants with SAE is <1.49% (one in every 67 participants).

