## **9.5.2 Safety Analysis Populations**

Safety summaries will be conducted in the APaT population, which consists of all participants who received study vaccine and had safety follow-up data after the vaccination.

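### Does the SAE bound of 1.49% in Section 9.9.2 conflict with the exact 95% CI planned in Section 9.6.2?

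*Combined protocol and SAP*

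**What the plan says.** Section 9.9.2 gives three statements about SAEs in 200 vaccinated participants: an 80% chance of seeing at least one if the true incidence is 0.80%, a 50% chance if it is 0.35%, and a bound for the zero-event case. The bound begins "If no SAEs are observed among the 200 participants" and continues that "this study will provide 95% confidence that the underlying percentage of participants with SAE is <1.49% (one in every 67 participants"). The section names no interval method and does not say whether the bound is one-sided or two-sided.

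Section 9.6.2 sets the reporting method: "The proportion of participants with AEs resulting in discontinuation from study and any SAEs will be reported and summarized descriptively", and "The point estimates and the 95% CIs will be calculated using the Clopper Pearson method". It has no separate rule for zero events.

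Section 9.5.2 defines the safety population (APaT) as "all participants who received study vaccine and had safety follow-up data after the vaccination".

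Section 9.9.1, on the primary endpoint, says that 200 participants "will allow estimation of the primary immunogenicity endpoint with a 95% CI with a half-width of 4.0 percentage points" if the response rate is 95%, and names Clopper-Pearson as the method.

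**The concern.** A reader of Section 9.9.2 would reasonably expect the report to show an upper limit of 1.49% if no SAE occurs. The interval planned in Section 9.6.2, on its ordinary two-sided reading, would show 0% to 1.83% for the same data and under the same 95% label. The reported limit is about 23% higher in relative terms, and nothing in the text explains the difference.

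The SAE rate that can be ruled out is the main precision statement for safety, and safety collection is limited to SAEs and AEs leading to discontinuation from the study. If 1.49% were wrong, or were the wrong quantity for the claim made, the protocol would overstate what a clean safety result shows in healthy children.

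A second worry is the denominator. The bound uses 200, while APaT requires both vaccination and safety follow-up, enrolment is only approximate, and Section 5.5 says that participants who withdraw are not replaced.

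**Working it through.** **Inputs.** n = 200 and x = 0 SAEs (Section 9.9.2); stated bound 1.49%, or 1 in 67 (Section 9.9.2); planned method Clopper-Pearson 95% (Section 9.6.2).

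**Formula.** With x = 0, the exact binomial upper limit p solves (1 − p)^n = t, where t is the upper-tail area. So p = 1 − t^(1/n).

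**Step 1: reproduce the plan's figure.** With t = 0.05: 1 − 0.05^(1/200) = 0.014867, or 1.49%; 1/0.014867 = 67.3. This matches the stated 1.49% and 1 in 67. The rule of three (3/200 = 1.50%) and the one-sided Wilson bound (1.33%) do not, so the figure is the exact one-sided 95% bound.

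**Step 2: check the rest of Section 9.9.2.**
- 1 − (1 − 0.0080)^200 = 79.9%, stated as 80%.
- 1 − (1 − 0.0035)^200 = 50.4%, stated as 50%.

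**Step 3: the planned interval for 0/200.** With t = 0.025: 1 − 0.025^(1/200) = 0.018275, or 1.83%; 1/0.018275 = 54.7. The two-sided interval is 0% to 1.83%, about 1 in 55 at the upper limit.

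**Step 4: is two-sided the right reading of Section 9.6.2?** The section does not use the word, but the n = 200 row of Table 3 in Section 9.9.1 shows which tails the plan uses with this method. Estimate minus lower limit, in percentage points:

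| Responders | 2.5% tail | 5% tail | Table 3 |
|---|---|---|---|
| 170/200 | 5.72 | 4.79 | 5.7 |
| 180/200 | 5.02 | 4.20 | 5.0 |
| 190/200 | 4.00 | 3.33 | 4.0 |

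The 2.5% tails match, so a two-sided reading of the 95% CI in Section 9.6.2 is well supported.

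**Step 5: compare like with like.** The difference is 1.828 − 1.487 = 0.341 percentage points; the ratio is 1.828/1.487 = 1.23. The chance of no SAE in 200 is 5.0% at a true rate of 1.487% and 2.5% at a true rate of 1.828%. The two limits therefore answer the same question at 95% and at 97.5% confidence in the upward direction. Neither corrects the other.

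**Step 6: denominator.** The documents give no attrition rate for the safety population. Taking 190 in APaT purely as an assumption, the one-sided bound is 1 − 0.05^(1/190) = 1.56% and the two-sided limit is 1 − 0.025^(1/190) = 1.92%. Losing 10 participants moves the one-sided bound by 0.07 to 0.08 points.

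**The case for a change.** The best argument for a change is consistency. Sections 9.9.1 and 9.9.2 are adjacent and use 95% with different tail areas, and neither says so. If no SAE occurs, a reader who sets the protocol beside the report will find 1.49% in one and 1.83% in the other, and must work out the reason. One sentence would remove the puzzle.

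The observation about labelling stands: the word one-sided is absent, and the two numbers would differ.

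The stronger claim, that the excludable rate is understated, does not stand. Section 9.9.2 does not describe a confidence interval. It states, with 95% confidence, that the rate lies below a value, and with zero events the exact value for that statement is 1.49%. It also does not say that this bound is what the report will tabulate; that is the job of Section 9.6.2. Putting 1.83% in its place would be a choice of convention.

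The denominator argument does not stand either. The sentence is conditional on 200 participants, and the section opens by saying that the probability of seeing an SAE depends on how many are vaccinated. It makes no forecast that every enrolled child will enter APaT.

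**Conclusion.** No change to the plan is needed. The 1.49% is correctly calculated and correctly worded as a one-sided 95% upper bound for 0/200. The 1.83% is the upper limit of the two-sided Clopper-Pearson interval that Section 9.6.2 would produce. They differ by 0.34 percentage points because one leaves 5% in the upper tail and the other 2.5%.

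Followed as written, the plan reports a sound interval of 0% to 1.83% if all 200 are in APaT and no SAE occurs, and the sentence in Section 9.9.2 remains true beside it. Safety is summarised descriptively, Section 9.3 rules out formal hypothesis testing, Section 4.4.1 sets no stopping criterion, and the sample size is presented through the precision of the immunogenicity endpoint. No decision turns on a value between 1.49% and 1.83%. The missing label is a detail that an analyst or report writer can supply without altering any result.

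This rests on two points: that the 95% CI in Section 9.6.2 is two-sided, which is the usual meaning and agrees with Table 3; and that the bound is read, as it is written, as conditional on 200 participants and no SAEs.

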## **9.10 Subgroup Analyses**

For both primary and secondary immunogenicity endpoints, the point estimates will be calculated by subgroup of prior Vaxelis® schedule, respectively (ie, 3 + 1 schedule in Protocol V419-007, 2 + 1 schedule in Protocol V419-008). The point estimates and corresponding 95% CIs will be reported for each subgroup.

## **9.11 Compliance (Medication Adherence)**

Given that participants will receive just a single dose of HBVAXPRO™, compliance will not be calculated.

## **9.12 Extent of Exposure**

The extent of exposure will be summarized by the number and proportion of subjects vaccinated with HBVAXPRO™.

## 10 SUPPORTING DOCUMENTATION AND OPERATIONAL CONSIDERATIONS

### 10.1 Appendix 1: Regulatory, Ethical, and Study Oversight Considerations

#### 10.1.1 Code of Conduct for Clinical Trials

Merck Sharp and Dohme Corp., a subsidiary of Merck & Co., Inc. (MSD)

#### Code of Conduct for Interventional Clinical Trials

##### I. Introduction

###### A. Purpose

MSD, through its subsidiaries, conducts clinical trials worldwide to evaluate the safety and effectiveness of our products. As such, we are committed to designing, implementing, conducting, analyzing, and reporting these trials in compliance with the highest ethical and scientific standards. Protection of participants in clinical trials is the overriding concern in the design and conduct of clinical trials. In all cases, MSD clinical trials will be conducted in compliance with local and/or national regulations, (including all applicable data protection laws and regulations), and International Council for Harmonisation Good Clinical Practice (ICH-GCP), and also in accordance with the ethical principles that have their origin in the Declaration of Helsinki.

###### B. Scope

Highest ethical and scientific standards shall be endorsed for all clinical interventional investigations sponsored by MSD irrespective of the party (parties) employed for their execution (e.g., contract research organizations, collaborative research efforts). This Code is not intended to apply to trials that are observational in nature, or which are retrospective. Further, this Code does not apply to investigator-initiated trials, which are not under the full control of MSD.

##### II. Scientific Issues

###### A. Trial Conduct

###### 1. Trial Design

Except for pilot or estimation trials, clinical trial protocols will be hypothesis-driven to assess safety, efficacy and/or pharmacokinetic or pharmacodynamic indices of MSD or comparator products. Alternatively, MSD may conduct outcomes research trials, trials to assess or validate various endpoint measures, or trials to determine patient preferences, etc.

The design (i.e., participant population, duration, statistical power) must be adequate to address the specific purpose of the trial and shall respect the data protection rights of all participants, trial site staff and, where applicable, third parties. Participants must meet protocol entry criteria to be enrolled in the trial.

###### 2. Site Selection

MSD selects investigative sites based on medical expertise, access to appropriate participants, adequacy of facilities and staff, previous performance in clinical trials, as well as budgetary considerations. Prior to trial initiation, sites are evaluated by MSD personnel (or individuals acting on behalf of MSD) to assess the ability to successfully conduct the trial.

###### 3. Site Monitoring/Scientific Integrity

Investigative trial sites are monitored to assess compliance with the trial protocol and Good Clinical Practice (GCP). MSD reviews clinical data for accuracy, completeness, and consistency. Data are verified versus

source documentation according to standard operating procedures. Per MSD policies and procedures, if fraud, scientific/research misconduct or serious GCP-non-compliance is suspected, the issues are investigated. When necessary, the clinical site will be closed, the responsible regulatory authorities and ethics review committees notified.

#### **B. Publication and Authorship**

Regardless of trial outcome, MSD commits to publish the primary and secondary results of its registered trials of marketed products in which treatment is assigned, according to the pre-specified plans for data analysis. To the extent scientifically appropriate, MSD seeks to publish the results of other analyses it conducts that are important to patients, physicians, and payers. Some early phase or pilot trials are intended to be hypothesis-generating rather than hypothesis testing; in such cases, publication of results may not be appropriate since the trial may be underpowered and the analyses complicated by statistical issues such as multiplicity.

MSD's policy on authorship is consistent with the recommendations published by the International Committee of Medical Journal Editors (ICMJE). In summary, authorship should reflect significant contribution to the design and conduct of the trial, performance or interpretation of the analysis, and/or writing of the manuscript. All named authors must be able to defend the trial results and conclusions. MSD funding of a trial will be acknowledged in publications.

### **III. Participant Protection**

#### **A. Regulatory Authority and Ethics Committee Review (Institutional Review Board [IRB]/Independent Ethics Committee [IEC])**

All protocols and protocol amendments will be submitted by MSD for regulatory authority acceptance/authorization prior to implementation of the trial or amendment, in compliance with local and/or national regulations.

The protocol, protocol amendment(s), informed consent form, investigator's brochure, and other relevant trial documents must be reviewed and approved by an IRB/IEC before being implemented at each site, in compliance with local and/or national regulations. Changes to the protocol that are required urgently to eliminate an immediate hazard and to protect participant safety may be enacted in anticipation of ethics committee approval. MSD will inform regulatory authorities of such new measures to protect participant safety, in compliance with local and/or national regulations.

